The University of Texas Medical Branch Galveston
Research Protocol

**Estimating Blood Loss Using Triton™ in Vaginal Deliveries: A Validation Trial
(ELUSIVE Trial)**

Principal Investigator: [name]

Co-Investigators: [name], CNM, & [name].

Funding: Department of Maternal Fetal Medicine

1. Introduction/Background/Purpose:

Postpartum hemorrhage (PPH) is the leading cause of maternal mortality in low-income countries and the primary cause of nearly one quarter of all maternal deaths globally (1). An estimated blood loss (EBL) in excess of 500 mL following a vaginal birth has often been used for the definition of PPH, but the average volume of blood lost at delivery can approach these amounts when actually measured rather than estimated (2). More than half of all maternal deaths occur within 24 hours of delivery, most commonly from excessive bleeding (3). Worldwide, 140,000 women succumb to postpartum hemorrhage each year. The most common antecedents to postpartum hemorrhage are uterine atony, placental disorders, and trauma during delivery. Improving maternal health worldwide is one of the WHO's 8 Millennium Development Goals. The prevention and treatment of PPH is an essential step towards the achievement of that goal (4).

Estimates of blood loss at delivery are notoriously inaccurate, with under-estimation more common than over-estimation (5). Traditionally, the clinicians performing the vaginal delivery would estimate the blood loss by visually assessing the blood collected in the delivery drape drain and counting the number of lap sponges used thru out the delivery. Current detection and management of hemorrhage is heavily based on clinical judgment, which often leads to delay in recognition and intervention. Often, interventions such as fluid resuscitation and blood transfusion are not initiated until significant hemorrhage has already taken place. The traditional method for estimating blood loss is based on the clinician and nursing staff's subjective assessment that is severely limited by human error and the presence of large volumes of amniotic fluid (6).

Early detection and treatment of this potentially life-threatening obstetric complication is of utmost importance in the field of obstetrics. Simulations and didactic training have been shown to improve visual estimations, but there are still poor associations between experience level and accuracy, and a significant decay in blood loss estimation skills over time (7).

The Triton L&D system (Gauss Surgical, Inc., Menlo Park, CA) is an FDA-cleared mobile application on a tablet computer (iPad) that facilitates quantification of blood loss (QBL) by providing an easy to use process and user interface. Dry weights of all potential blood containing substrates are built-in to the device allowing batch weighing with automatic subtraction of dry weights. There is also a V-drape simulator accounting for collected fluids with automatic subtraction of a measured amount of amniotic fluid.

QBL is not regularly used at UTMB. Although widely recommended, little data is available to support its use in the obstetrical population. We believe that gathering further evidence regarding its value is appropriate.

Our hypothesis is that use of this device for QBL will enable clinicians to objectively measure blood loss in real-time.

This study will be a prospective cohort study, in which we will evaluate two methods of evaluating blood loss during vaginal delivery (usual visual EBL assessment versus Device QBL). Of note, the subjects consented will be used as self-controls.

2. **Summary of project:** This study will be a prospective cohort study. Patients who meet criteria for inclusion in the study will be approached for participation at same day of admission. Written informed consent will be obtained from the patients by the Co-PI and by the study collaborators. If patients agree to participate, a CBC (complete blood count) will be obtained via venous puncture routine in our facility as part of the admission labs which will be around 10 cc of blood. The device will be used during the delivery in laboring room. The device will be used to assess QBL by the research staff only and results/ QBL assessment will be masked to the clinical team. Unmasking will only occur following study completion with purpose to perform data analysis. Patient management will be according to the clinical team without the knowledge of the QBL. All patients undergo a CBC postpartum as part of post-partum evaluation, this will also be performed by venipuncture where 10 cc of blood will be collected. The drop in Hgb (Δ Hgb) between the pre and post partum CBCs will be calculated for each patient. The post-partum CBC will be collected approximately 24-30 hours from delivery as standard in our unit. The blood will be collected from each patient by the nursing staff who are experienced in withdrawing blood. Patients will be divided into quartiles of Δ Hgb. Cases will be those patients whose Δ Hgb is in the upper quartile, while controls will be those patients whose Δ Hgb is in the lower 3 quartiles. We will be comparing visual EBL by standard clinical assessment versus the QBL result from the device between cases and controls.

The Triton L&D system which comprises of the device, software analysis and staff training will be supplied by the manufacturer free of charge. Research staff will be trained by the manufacturer. We will be offering our skills, fellows, midwives and residents, who will be collecting data and we will be performing the data analysis. Results will be available to the manufacturer after results are completed. The results of this study will be presented in conferences or published in a peer-review journal.

Demographic information will be obtained from the electronic medical record. The data will be kept on a password secured UTMB computer. An encrypted USB flash drive will be used to transfer data. The data will be identified and linked to the patient using the medical record number (MRN). During data analysis, all patient identifiers will be deleted.

3. Study procedures: VISIT#1

3.1 Screening, Recruitment and Consenting: When a patient meets inclusion criteria for participation in our study, the obstetrical team will contact the research team. Written informed consent will be obtained from the patient by the PI, study coordinator, or collaborator. Study participation will be completed when the patient is discharged from the hospital. The data collected will be kept on a password secured UTMB computer. An encrypted USB flash drive will be used to transfer data. The data will be linked via MRN, which is needed to access the demographic data and will be deleted when the data is analyzed. Our target sample size is 556 subjects.

3.2. Baseline procedures: In some patients, there will be no baseline procedures aside from using the masked device for assessment of QBL. Every effort will be made to mask the clinical staff from the QBL information so as not to affect the standard assessment of visual EBL and medical decision making. During blood loss assessment, clinicians will be instructed not to place any sponges and other junk or materials into the calibrated v-drape following placental delivery (before placenta is delivered this is allowed), since it can artificially inflate or interfere with the accuracy of QBL. Subjects, where this protocol deviation occurs, will be removed from the final analysis and replaced by other cases in order to meet our final sample size. Neither the subject's insurance nor the subject will be responsible for any charges relating to tests done only for research.

3.3. Study visits/Follow-up: One study visit will be needed during the trial. The subject participation will be considered complete when the subject is discharged home.

3.6. Withdrawals: Subjects who withdraw from the study after inclusion will be excluded from further follow-up. Data collected until the time of withdrawal will be analyzed.

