3.7 Outcomes

- **Primary outcome:** Differences in blood loss between cases and controls using clinical estimate (visual EBL) versus device assessment (QBL).
- **Secondary outcomes:** System performance (ROC sensitivity analysis and correlation). Delta hemoglobin, hemorrhage recognition (defined as >500 ml blood loss), transfusion requirements (timing, rate, dose, etc.), administration of uterotronics, colloid resuscitation, post-partum hemorrhage or hemorrhagic shock.

4. Criteria for inclusion of subjects:

Pregnant women between the ages of 18-50.
Plan of care is vaginal delivery.

5. Criteria for exclusion of subjects:

- Incarcerated patients.
- Patient unwilling or unable to provide consent.
- Intrauterine fetal demise (no fetal heart beat identified and documented by two physicians).
- Placenta previa or other known placental anomalies.
- Any contraindications to vaginal delivery.
- Enrolled in another trial that may affect outcome.

6. Sources of research material: Electronic medical records.

7. Recruitment methods and consenting process: See 3.1 above.

8. Potential risks

8.1 Loss of confidentiality: Any time information is collected, there is a potential risk for loss of confidentiality. Every effort will be made to keep the subject's information confidential; however, this cannot be guaranteed.

9. Potential benefits: With the QBL approach of assessing blood loss more objectively during vaginal delivery, there are many potential benefits to future patients, including: decrease in the delay in diagnosis of hemorrhagic shock, decrease in delay in interventions and improved postpartum surveillance. In addition, this data will be useful in designing a level 1 trial to measure outcomes such as transfusion rates, transfusion complications, hemorrhage and maternal death.

10. Data monitoring: The PI, research coordinator, and collaborators will ensure that all aspects of data quality adhere to the study design. This will include monitoring for adherence to consent procedures, inclusion and exclusion criteria, valid abstraction, correct entry, timeliness and

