responsiveness to data queries. Data will be collected and stored with the participant ID code only. The master enrollment log linking patient identifiers with study ID numbers will be kept in a password protected database on the Ob/Gyn department's internal server. Several data collection forms will be used. Data on these forms will be devoid of personal identifiers and will be securely stored at the division offices. The research coordinator will be available to monitor the data and correct any discrepancies based on source documents if needed.

11. Procedures to maintain confidentiality: Each subject will be assigned a study number with personally identifiable information deleted or removed. If needed, charts will be reviewed in the medical records area. Subjects' information will be de-identified and tagged with a number. Data will be collected and stored on a UTMB password-protected computer.

Statistical approach: We will be performing a prospective study. After defining cases and controls using the cutoff of upper quartile for pre- to postop- hemoglobin drop. We will use univariable and multivariable analysis to check for association between both blood loss assessment techniques using the device and the subjective clinical assessment among our cases and controls. We will be comparing cases versus controls (two groups) and EBL/QBL (continuous variable and primary outcome) hence t tests/means were used for our sample calculation; For the purpose of the study, we believe a sample size of 500 will be able to evaluate our primary outcome. Accounting for 10% loss of data or follow-up: **N total is 556 subjects.** This was based on a study of 30,937 patients having vaginal deliveries using the Triton™ System (the mean measured blood loss was 383.87ml with a standard deviation of 330.52 ml (unpublished data supplied by the manufacturer). For a power of 80% and alpha of 0.05 and 25% effect size 1: 3 allocation (25%ile versus 75%ile PP delta hemoglobin):

Estimated sample sizes for a two-sample means test
t test assuming $sd_1 = sd_2 = sd$
 $H_0: m_2 = m_1$ versus $H_a: m_2 \neq m_1$

Study parameters:

```
alpha = 0.0500
power = 0.8000
delta = -95.9700
m1 = 383.8700
m2 = 287.9000
sd = 330.5200
N2/N1 = 3.0000
```

Estimated sample sizes:

N = 500
N1 = 125
N2 = 375

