We will also be using multiple model correlation (correlation coefficient) (secondary outcome) between QBL Device and EBL Standard. We will also perform ROC curve analysis (secondary outcome) to compare the area under the curve (AUC) to predict Δ Hgb in the upper quartile by clinical estimate versus device assessment. The coefficient of multiple correlation takes values between 0 and 1; a higher value indicates a better predictability of the dependent variable (QBL Device) from the independent variable (EBL standard).

REFERENCES

1. AbouZahr, C. (2003). Global burden of maternal death and disability. *Br Med Bull*, 67, 1-11.
2. Chesley, L. C. (1972). Plasma and red cell volumes during pregnancy. *Am J Obstet Gynecol*, 112(3), 440-450.
4. WHO Guidelines Approved by the Guidelines Review Committee: WHO recommendations for the prevention and treatment of postpartum hemorrhage. Geneva, Switzerland, 2012.
5. Bonnet, M. P., & Benhamou, D. (2016). Management of postpartum haemorrhage. *F1000Res*, 5. doi:10.12688/f1000research.7836.1.
6. Satish, Siddarth MS; Deckers, Elizabeth A. MD; Philip, Bridget M. MD; Ting, Vicki MD; Weinberg, Joseph T. BA. Novel System for Rapid Assessment of Blood Loss in Elective Surgery and Cesarean Delivery. *Obstet Gynecol*. 2014 May;123 Suppl 1:170S.
7. Dildy, G. A., 3rd, Paine, A. R., George, N. C., & Velasco, C. (2004). Estimating blood loss: can teaching significantly improve visual estimation? *Obstet Gynecol*, 104(3), 601-606. doi:10.1097/01.aog.0000137873.07820.34.
10. Holmes, A. A., Konig, G., Ting, V., Philip, B., Puzio, T., Satish, S., & Waters, J. H. (2014). Clinical evaluation of a novel system for monitoring surgical hemoglobin loss. *Anesth Analg*, 119(3), 588-594. doi:10.1213/ane.000000000000181.

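### Optional improvement, not an error: add a comparison of QBL and EBL against uncut ΔHgb, and report QBL-EBL agreement in mL in place of a correlation

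*Combined protocol and SAP*

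**What the plan says.** ΔHgb comes from the admission and post-partum blood counts and is available as a continuous value for each woman (Section 2, Summary of project). Three described analyses use it, all after a cut at the 75th percentile:

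- The case-control contrast in Section 2, which is also the primary outcome in Section 3.7: "Cases will be those patients whose Δ Hgb is in the upper quartile".
- The univariable and multivariable models in the Statistical approach, which follow "After defining cases and controls using the cutoff of upper quartile for pre- to postop- hemoglobin drop".
- The ROC analysis in the closing part of the Statistical approach, which is planned "to compare the area under the curve (AUC) to predict Δ Hgb in the upper quartile by clinical estimate versus device assessment".

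Section 3.7 also lists ΔHgb, uncut, as a secondary outcome, next to "System performance (ROC sensitivity analysis and correlation". It attaches no analysis to ΔHgb and names no variables for the correlation. The Statistical approach names them once: "We will also be using multiple model correlation (correlation coefficient) (secondary outcome) between QBL Device and EBL Standard". It reads a higher coefficient as better prediction of QBL from EBL. It names no mean difference or limits of agreement between the two methods.

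Transfusion is another secondary outcome in Section 3.7. The text does not say how transfused women enter the ΔHgb analyses.

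**The concern.** The trial is presented as a validation of the device, with each woman assessed by both methods. The natural head-to-head question is which method follows the hemoglobin drop more closely. ΔHgb is the only reference against which the plan compares both methods, and no power is stated for that question.

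Two things are at stake. First, a cut at the upper quartile treats a woman just above the cut like one far above it, and treats all women below it alike. If blood loss and ΔHgb are related throughout, the AUC comparison is less precise than the data allow.

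Second, the named QBL-EBL coefficient cannot fill the gap. With one predictor, a multiple correlation is the absolute value of the ordinary correlation. It is the same in either direction, does not involve ΔHgb, and is blind to proportional error. The Introduction says that under-estimation is the more common error in judging blood loss, so a measure that cannot show it is a weak sole summary of how the methods compare.

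**Working it through.** **1. The plan's own figure.** Inputs from the Statistical approach: means 383.87 and 287.90 mL (difference 95.97), SD 330.52, two-sided alpha 0.05, power 0.80, allocation 1:3, losses 10%.

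- N1 = (1 + 1/3) × (1.960 + 0.842)² × (330.52/95.97)² = 1.333 × 7.849 × 11.861 = 124.1, so 125. N2 = 375 and N = 500.
- Exact power at 125/375 from the noncentral t is 0.801. 500/0.90 = 555.6, so 556.

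The stated figures reproduce.

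**2. Information kept by the cut.** For a normal variable cut so that a fraction p lies above, the fraction kept is φ(z)²/[p(1−p)]. With p = 0.25, z = 0.6745 and φ(z) = 0.3178: 0.3178²/0.1875 = 0.539. Other assumed shapes of ΔHgb, still with a linear relation, give 0.51 (logistic), 0.56 (uniform), 0.61 (lognormal) and 0.64 (exponential).

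**3. Head-to-head power at N = 500.** The documents give no correlations, so these are assumptions, with a latent normal relation. The planned comparison is taken as the DeLong test of two paired AUCs. The alternative is the Williams test on ranks:

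t = (r1 − r2) × √{(n−1)(1+r12) / [2((n−1)/(n−3))D + r̄²(1−r12)³]}, where D = 1 − r1² − r2² − r12² + 2·r1·r2·r12 and r̄ is the mean of r1 and r2.

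Simulated power (ranges over repeat runs):

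| QBL-ΔHgb / EBL-ΔHgb / QBL-EBL | AUC comparison | Rank comparison |
|---|---|---|
| 0.40 / 0.25 / 0.6 | 78-80% | 96-98% |
| 0.30 / 0.15 / 0.5 | 66-69% | 90-91% |
| 0.40 / 0.30 / 0.5 | 38-39% | 62-64% |
| 0.25 / 0.25 / 0.5 (no difference) | about 5% | about 5% |

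Hand check of the first row. Spearman = (6/π)·arcsin(r/2) turns 0.40, 0.25 and 0.6 into 0.385, 0.239 and 0.582. Then D = 0.563, and t = 0.145 × √(499 × 1.582)/√1.138 = 3.82. Power is about Φ(3.82 − 1.96) = 0.97, in line with the simulation.

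**4. Does the gain depend on the shape of the relation?** Assumed model: true loss lognormal with the protocol's mean and SD; QBL and EBL equal to log loss plus normal error, with two pairs of error SDs on the standardised log scale. Power for AUC / rank comparison:

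| ΔHgb responds to | Error SD 0.5 vs 1.0 | Error SD 0.6 vs 0.9 |
|---|---|---|
| log loss | 42% / 69% | 22% / 35% |
| mL of loss | 44% / 59% | 20% / 26% |
| loss above 300 mL only | 94% / 93% | 57% / 56% |
| loss above 500 mL only | 47% / 42% | 20% / 18% |
| loss above 700 mL only | 16% / 14% | 9% / 7% |

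The levels depend on how much unrelated variation ΔHgb is given, so only the two figures within a cell should be compared. Another set of assumed models gave 30% / 41% for mL and 13% / 13% above 500 mL. The gain is clear in the first row, smaller in the second, and gone once only larger losses matter.

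**5. Transfused women.** Assume that 2% of women have ΔHgb blunted by 1.5 SD in line with one method only. With equal true correlations, the rank test then rejects 6.2-7.1% of the time and the AUC test 5.7-6.3%. Excluding those women brings the rank test to 5.5%.

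**6. What the QBL-EBL coefficient misses.** If EBL = 0.6 × QBL exactly, the coefficient is 1.0. At a mean QBL of 383.87 mL the mean gap is 0.4 × 383.87 = 154 mL.

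**The case against.** The strongest reply is that the two analyses answer different questions. The plan is about hemorrhage, and the upper quartile points at large drops. Rank correlation gives weight to the whole range, including drops of no clinical interest, so a power comparison between them is not purely one of efficiency. That stands, and it is why the addition should supplement the quartile analysis and not replace it. Step 4 supports the same reply: if small losses do not move Hgb, the cut costs nothing.

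It can also be said that Section 3.7 lists both ΔHgb and correlation, so a correlation with ΔHgb may be intended. That is possible. The listing specifies no such analysis, however, so at the least the wording has a gap.

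On agreement, the Section 2 comparison may well report mean EBL and mean QBL by group, from which an average gap could be read. It would not show the spread of individual differences.

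A reader might go further and infer that the plan discards half its information, or that the AUC comparison needs about 950 women to match the rank test at 500. Both hold only under the latent normal model of step 3. The documents give neither the distribution of ΔHgb nor the shape or strength of its relation to blood loss, so neither can be stated as a fact about this trial.

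**Conclusion.** The point holds as an optional improvement. No described analysis relates QBL or EBL to uncut ΔHgb, although all three are recorded for each woman. If ΔHgb is near-normal and roughly linearly related to loss over its whole range, the cut keeps about 54% of the information, and head-to-head power rises from about 79% to 96% in the most favorable assumed case. In the least favorable of the three it rises from about 38% to 63%, still short of 80%. The gain shrinks if Hgb falls in proportion to mL and vanishes if only large losses move it.

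The remark on the QBL-EBL coefficient rests on algebra and needs no such assumption: it cannot detect proportional under-estimation.

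A reader might infer that the sample size or the primary contrast is faulty. The documents do not support that, since 500 and 556 follow from the stated inputs and neither depends on this point. Nor would a mean QBL-EBL gap show which method is biased, because the plan has no measure of true blood loss.

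**What to change.** In the Statistical approach, before unmasking:

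1. Keep the upper-quartile contrast and the ROC comparison. Add, as a prespecified secondary analysis, the Spearman correlations of QBL and of EBL with continuous ΔHgb, and a paired test of their difference (Williams on ranks, or a paired bootstrap).
2. Repeat that comparison without transfused women as a sensitivity analysis, and report both results. Section 2 states that "Patient management will be according to the clinical team without the knowledge of the QBL", so transfusion may follow the visual estimate more closely than the device reading.
3. In place of the QBL-EBL multiple correlation, report the mean difference with 95% limits of agreement, on a log or ratio scale if the spread grows with volume. Describe it as agreement and not as proof of which method is biased.

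The cost is a few sentences of SAP text and a few lines of analysis on data already collected. A difference in rank correlations is less intuitive than a case-control contrast and weighs all of ΔHgb, so it should be labelled as supplementary. No change to the sample size or study procedures follows.

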3.7 Outcomes

- **Primary outcome:** Differences in blood loss between cases and controls using clinical estimate (visual EBL) versus device assessment (QBL).
- **Secondary outcomes:** System performance (ROC sensitivity analysis and correlation). Delta hemoglobin, hemorrhage recognition (defined as >500 ml blood loss), transfusion requirements (timing, rate, dose, etc.), administration of uterotronics, colloid resuscitation, post-partum hemorrhage or hemorrhagic shock.

4. Criteria for inclusion of subjects:

Pregnant women between the ages of 18-50.
Plan of care is vaginal delivery.

5. Criteria for exclusion of subjects:

- Incarcerated patients.
- Patient unwilling or unable to provide consent.
- Intrauterine fetal demise (no fetal heart beat identified and documented by two physicians).
- Placenta previa or other known placental anomalies.
- Any contraindications to vaginal delivery.
- Enrolled in another trial that may affect outcome.

6. Sources of research material: Electronic medical records.

7. Recruitment methods and consenting process: See 3.1 above.

8. Potential risks

8.1 Loss of confidentiality: Any time information is collected, there is a potential risk for loss of confidentiality. Every effort will be made to keep the subject's information confidential; however, this cannot be guaranteed.

9. Potential benefits: With the QBL approach of assessing blood loss more objectively during vaginal delivery, there are many potential benefits to future patients, including: decrease in the delay in diagnosis of hemorrhagic shock, decrease in delay in interventions and improved postpartum surveillance. In addition, this data will be useful in designing a level 1 trial to measure outcomes such as transfusion rates, transfusion complications, hemorrhage and maternal death.

10. Data monitoring: The PI, research coordinator, and collaborators will ensure that all aspects of data quality adhere to the study design. This will include monitoring for adherence to consent procedures, inclusion and exclusion criteria, valid abstraction, correct entry, timeliness and

responsiveness to data queries. Data will be collected and stored with the participant ID code only. The master enrollment log linking patient identifiers with study ID numbers will be kept in a password protected database on the Ob/Gyn department's internal server. Several data collection forms will be used. Data on these forms will be devoid of personal identifiers and will be securely stored at the division offices. The research coordinator will be available to monitor the data and correct any discrepancies based on source documents if needed.

11. Procedures to maintain confidentiality: Each subject will be assigned a study number with personally identifiable information deleted or removed. If needed, charts will be reviewed in the medical records area. Subjects' information will be de-identified and tagged with a number. Data will be collected and stored on a UTMB password-protected computer.

Statistical approach: We will be performing a prospective study. After defining cases and controls using the cutoff of upper quartile for pre- to postop- hemoglobin drop. We will use univariable and multivariable analysis to check for association between both blood loss assessment techniques using the device and the subjective clinical assessment among our cases and controls. We will be comparing cases versus controls (two groups) and EBL/QBL (continuous variable and primary outcome) hence t tests/means were used for our sample calculation; For the purpose of the study, we believe a sample size of 500 will be able to evaluate our primary outcome. Accounting for 10% loss of data or follow-up: **N total is 556 subjects.** This was based on a study of 30,937 patients having vaginal deliveries using the Triton™ System (the mean measured blood loss was 383.87ml with a standard deviation of 330.52 ml (unpublished data supplied by the manufacturer). For a power of 80% and alpha of 0.05 and 25% effect size 1: 3 allocation (25%ile versus 75%ile PP delta hemoglobin):

Estimated sample sizes for a two-sample means test
t test assuming $sd_1 = sd_2 = sd$
 $H_0: m_2 = m_1$ versus $H_a: m_2 \neq m_1$

Study parameters:

```
alpha = 0.0500
power = 0.8000
delta = -95.9700
m1 = 383.8700
m2 = 287.9000
sd = 330.5200
N2/N1 = 3.0000
```

Estimated sample sizes:

N = 500
N1 = 125
N2 = 375

We will also be using multiple model correlation (correlation coefficient) (secondary outcome) between QBL Device and EBL Standard. We will also perform ROC curve analysis (secondary outcome) to compare the area under the curve (AUC) to predict Δ Hgb in the upper quartile by clinical estimate versus device assessment. The coefficient of multiple correlation takes values between 0 and 1; a higher value indicates a better predictability of the dependent variable (QBL Device) from the independent variable (EBL standard).

REFERENCES

1. AbouZahr, C. (2003). Global burden of maternal death and disability. *Br Med Bull*, 67, 1-11.
2. Chesley, L. C. (1972). Plasma and red cell volumes during pregnancy. *Am J Obstet Gynecol*, 112(3), 440-450.
4. WHO Guidelines Approved by the Guidelines Review Committee: WHO recommendations for the prevention and treatment of postpartum hemorrhage. Geneva, Switzerland, 2012.
5. Bonnet, M. P., & Benhamou, D. (2016). Management of postpartum haemorrhage. *F1000Res*, 5. doi:10.12688/f1000research.7836.1.
6. Satish, Siddarth MS; Deckers, Elizabeth A. MD; Philip, Bridget M. MD; Ting, Vicki MD; Weinberg, Joseph T. BA. Novel System for Rapid Assessment of Blood Loss in Elective Surgery and Cesarean Delivery. *Obstet Gynecol*. 2014 May;123 Suppl 1:170S.
7. Dildy, G. A., 3rd, Paine, A. R., George, N. C., & Velasco, C. (2004). Estimating blood loss: can teaching significantly improve visual estimation? *Obstet Gynecol*, 104(3), 601-606. doi:10.1097/01.aog.0000137873.07820.34.
10. Holmes, A. A., Konig, G., Ting, V., Philip, B., Puzio, T., Satish, S., & Waters, J. H. (2014). Clinical evaluation of a novel system for monitoring surgical hemoglobin loss. *Anesth Analg*, 119(3), 588-594. doi:10.1213/ane.000000000000181.

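### The 80% power claimed for the primary outcome covers one case-control t test on device-type data; it does not cover visual EBL or the EBL-versus-QBL contrast, for which the primary outcome names no test

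*Combined protocol and SAP*

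**What the plan says.** - **Framing.** Section 1 describes two ways of assessing blood loss in the same women, who act as their own controls. Section 2 adds: "We will be comparing visual EBL by standard clinical assessment versus the QBL result from the device between cases and controls". Cases are women in the upper quartile of haemoglobin drop; controls are the other three quartiles.
- **Primary outcome (section 3.7).** "Differences in blood loss between cases and controls using clinical estimate (visual EBL) versus device assessment (QBL").
- **Sample size (Statistical approach).** "we believe a sample size of 500 will be able to evaluate our primary outcome". The reason given for the method is that the comparison is of "cases versus controls (two groups) and EBL/QBL (continuous variable and primary outcome) hence t tests/means were used for our sample calculation". The inputs are described as follows: "the mean measured blood loss was 383.87ml with a standard deviation of 330.52 ml (unpublished data supplied by the manufacturer"). The calculation uses m1 = 383.87, m2 = 287.90, SD = 330.52, a 1:3 ratio, two-sided alpha 0.05 and power 0.80, giving 125 + 375 = 500, raised to 556 for 10% loss.
- **Analysis covering both methods (Statistical approach).** "We will use univariable and multivariable analysis to check for association between both blood loss assessment techniques", with no model, contrast or test specified.
- **Secondary analyses.** Section 3.7 lists "System performance (ROC sensitivity analysis and correlation"). The end of the Statistical approach says "We will also perform ROC curve analysis (secondary outcome) to compare the area under the curve (AUC") for predicting the upper quartile of haemoglobin drop by each method. It also plans a correlation between QBL and EBL. Neither has an expected value, interval width or power.

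**The concern.** The primary outcome contains two contrasts: cases against controls, and visual EBL against device QBL. The power statement is attached to the outcome as a whole, but only the first contrast enters the calculation, and only with device-derived inputs. No SD for EBL, case-control gap for EBL or EBL-QBL correlation appears anywhere.

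At stake is what the primary result can support. It could come out positive for both methods, or for one and not the other. Neither result shows whether the device separates cases from controls better than visual estimation does. If the between-method contrast is left open until unmasking, it can be chosen with the results in view.

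**Working it through.** **1. The plan's own figure.** Inputs from the Statistical approach: gap 95.97 mL, SD 330.52 mL, n = 125 and 375, two-sided alpha 0.05.

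SE = 330.52 × √(1/125 + 1/375) = 330.52 × 0.10328 = 34.14 mL. Noncentrality = 95.97 / 34.14 = 2.811. The noncentral t with 498 df gives power **0.801**. For loss, 500 / 0.90 = 555.6, so 556. The arithmetic is sound.

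**2. What the 80% depends on, even for QBL.** The source's overall mean, 383.87 mL, is entered as the mean of the case group. The implied overall mean is 0.25 × 383.87 + 0.75 × 287.90 = **311.9 mL**, not 383.87. The source's overall SD is used as the within-group SD. The 95.97 mL gap is 25% of 383.87, with no reason given for that fraction.

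**3. The same t test on EBL.** The documents give no EBL inputs, so these are assumptions, tested with the formula in step 1 at 125/375:

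| Assumed EBL gap (mL) | Assumed EBL SD (mL) | Power |
|---|---|---|
| 95.97 | 250 | 0.960 |
| 95.97 | 330.52 | 0.801 |
| 95.97 | 400 | 0.640 |
| 48 (half) | 330.52 | 0.289 |

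The 80% carries over to EBL only in the second row.

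**4. The between-method contrast.** In mL, the natural quantity is the case-control difference in D = QBL − EBL, with SD_D = √(SD_Q² + SD_E² − 2ρ·SD_Q·SD_E). Of its inputs, only SD_Q is in the documents; SD_E, ρ and the EBL gap are not. To show how much this matters, assume equal SDs and a 48 mL contrast. For ρ = 0.3, 0.5, 0.7 and 0.9, SD_D is 391.1, 330.5, 256.0 and 147.8 mL, and power is 22%, 29%, 44% and 88%. No single figure can be defended.

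**5. Why two t tests do not give a between-method test.** Suppose both methods have exactly the planned gap and SD, so neither is better. Take the two test statistics as bivariate normal with mean 2.811, unit variance and correlation ρ (within-group EBL-QBL correlation, assumed). Each is significant with probability 0.803. P(exactly one significant) = 2 × (0.803 − P(both)).

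| ρ | P(both significant) | P(exactly one significant) |
|---|---|---|
| 0.3 | 0.670 | 0.27 |
| 0.5 | 0.691 | 0.22 |
| 0.7 | 0.716 | 0.17 |
| 0.9 | 0.753 | 0.10 |

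Simulation of the t tests with normal outcomes gives 0.26, 0.23, 0.17 and 0.10.

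**6. What the planned AUC comparison can detect.** Binormal model, paired AUCs, 125/375, 80% power: detectable difference = 2.802 × SE(difference), solved iteratively because the SE depends on both AUCs. The EBL AUC and ρ are assumptions.

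| EBL AUC | ρ = 0.3 | 0.5 | 0.7 | 0.9 |
|---|---|---|---|---|
| 0.54 | 0.097 | 0.084 | 0.066 | 0.039 |
| 0.80 | 0.070 | 0.061 | 0.050 | 0.030 |

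For scale, the planned QBL gap corresponds to a binormal AUC of Φ(95.97 / (330.52 × √2)) = 0.58.

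**The case against.** The strongest reply is that there is little mismatch. The primary outcome says the difference is between cases and controls, and the Statistical approach names EBL/QBL as the continuous variable. Read together, the primary analysis is a case-control comparison run for each method, and a two-sample t test is the right test for that. A reader might infer that the wrong test was chosen or that N was miscalculated. The documents support neither: the t test fits the case-control half of the wording, and 500 and 556 reproduce.

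A reader might also infer that the plan will claim superiority when one t test is significant and the other is not. It nowhere says so. The stated hypothesis is that the device allows objective measurement in real time, not that it outperforms visual estimation. Nor is a between-method analysis missing altogether, because the AUC comparison is planned. Step 5 is therefore a reason to rule out that inference in advance, not a description of a planned analysis.

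What remains is narrower but real. Even with one t test per method, the 80% is supported for EBL only under an unstated assumption of equal SD and gap. No test for the EBL-versus-QBL part of the primary wording is named, and the analysis that could answer it is secondary. Lack of a precision statement for a secondary analysis is not in itself an error.

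**Conclusion.** The concern holds in limited form. The stated power belongs to one case-control t test on a device-type measure: 0.801, conditional on a 95.97 mL gap and a within-group SD of 330.52 mL. It would be too strong to call the 80% secure for QBL, given how the overall mean and SD were used. It is not power for EBL, where assumed inputs move it from 29% to 96%. It is not power for EBL versus QBL, which cannot be derived from the documents. The primary outcome names no between-method test, and a split between two t tests would arise in about 10% to 27% of trials with no true difference between methods (normal outcomes, equal gaps and SDs, ρ from 0.9 to 0.3).

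This should be fixed. It concerns the meaning of the primary result and its only power claim. It does not affect the design, enrolment or the correctness of N.

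**What to change.** 1. **Statistical approach, sample size.** Restate the 80% as power for a single case-control t test on QBL, conditional on an assumed gap of 95.97 mL and a within-group SD of 330.52 mL. Note that 383.87 mL is the source's overall mean but is used as the case mean (implied overall mean 311.9 mL). Say that the figure is not power for EBL or for EBL versus QBL.
2. **Section 3.7 and Statistical approach.** Reword the primary outcome as the case-control comparison that was sized. Make the paired difference AUC(QBL) − AUC(EBL), already planned, the key secondary outcome, with a DeLong test and 95% CI. State that any conclusion that the device does better or worse than visual estimation rests on that difference, and not on comparing the significance of two t tests. Making the AUC difference primary is open to the sponsor as a design choice but is not required.
3. **Optional.** If a detectable AUC difference is quoted, give its model and assumptions, as in step 6. Do not mix binormal results with lognormal results indexed by a latent correlation, because the two correlation scales differ.
4. **Interpretation.** State that a non-significant between-method difference will not be read as equivalence.

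Cost: protocol text only; enrolment and data collection do not change. The power claim becomes narrower, and the between-method result may be inconclusive with 500 women.
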